## 9.4 Evaluation of best overall response

Best overall response is the best response recorded from the start of radiation therapy until disease progression or recurrence, taking as reference for progressive disease the smallest measurements recorded since SABR.

Target Lesions	Non-Target Lesions	New Lesions	Overall Response
CR	CR	No	CR
CR	PR/SD	No	PR
PR	Non-PD	No	PR
SD	Non-PD	No	SD
PD	Any	Yes or No	PD
Any	PD	Yes or No	PD
Any	Any	Yes	PD

## 10. QUALITY OF LIFE ASSESSMENT

The FACT-G patient-reported quality of life (QOL) assessment instrument will be completed by all patients at the following time points:

- Screening 6 weeks ( $\pm 14$  days) after completion of SABR if the six weeks visit is being performed.
- 3 months ( $\pm 28$  days) after completion of SABR
- 6 months ( $\pm 28$  days) after completion of SABR
- 9 months ( $\pm 28$  days) after completion of SABR
- 12 months ( $\pm 28$  days) after completion of SABR

## 11. SAFETY ASSESSMENT

Safety parameters evaluated during this study will include AEs, vital signs, physical examination findings and clinical laboratory values. All safety parameters will be performed in accordance with the study calendar (Section 8.4).

### 11.1 Adverse Event definition, Assessment and Reporting

An Adverse Event (AE) is defined as any unfavorable medical occurrence in a human subject including any abnormal sign, symptom, or disease.

The term AE is used to include both serious and non-serious AEs related to the radiation therapy specifically delivered on this study. It should be noted that additional radiation therapy is permitted by this study protocol to other lesions than what is being treated on this study; the treating physician should use best clinical judgment about whether any AE may be related specifically to the treatment delivered on study.

The Investigator or qualified designee will assess each subject to evaluate for potential or new worsening AEs as specified in the Schedule of Assessment and more frequently if clinically indicated.

Adverse Events (AEs) will be graded and recorded throughout the trial using the Common Terminology Criteria for Adverse Events (CTCAE) v5.0 criteria.

A causal relationship between the radiation therapy delivered on this study and the AE should be determined with the treating physician using best clinical judgment to select one of the following for each AE:

- *Definitely related:* There is a definite relationship between study treatment and the AE. An alternative cause is highly unlikely. There is a strong time-based relationship between study treatment and the AE.
- *Probably related:* There is a reasonable probability that the AE is likely to have been caused by study treatment. The AE has a timely relationship to the study

treatment and follows a known pattern of response, but a potential alternative cause is possible.

- *Possibly related*: There is a possible relationship between the AE and study treatment. There may not be a known pattern of response and an alternative cause is more likely. A possible relationship between the AE and study treatment cannot be reasonably ruled out.
- *Unrelated*: There is not a reasonable causal relationship between study treatment and the AE. For example, the unrelated AE may be due to disease progression and not study treatment.

All AEs, regardless of the source of identification (e.g., physical examination, laboratory assessment, or reported by the patient), will be collected and recorded in the eCRF, upon initiation of treatment and for a minimum of 100 days after completion of radiation therapy or until resolution or stabilization or reported as SAEs if they become serious.

## 11.2 Serious adverse event definition and reporting

A serious adverse event (SAE) is an AE occurring during any study phase that fulfills one or more of the following criteria:

- Results in death;
- Is immediately life-threatening;
- Requires in-patient hospitalization or prolongation of existing hospitalization;
- Results in persistent or significant disability/incapacity;
- Is an important medical event that may jeopardize the patient or may require medical intervention to prevent one of the outcomes listed above

It is important to note that hospital admission for a planned medical/surgical procedure or disease treatment is not considered a SAE.

Only SAEs assessed by the investigator as related to any protocol-specific procedure or therapy will be collected and reported.

The investigator at each site must review source documentation and describe pertinent information, provide a causality assessment of the event documented in OnCore. The SAE form generated in OnCore must be printed, signed and dated by the investigator.

The study team will submit all SAEs to the MCI Multisite Research Program by email to: [[contact]](mailto:[contact]) within 24 business hours of becoming aware of the initial event.

After receipt of the initial report, the Sponsor-Investigator or designee will review the information and, if necessary, contact the site study team to obtain further information.

Information to be reported in the description of each adverse event may include, but is not limited to:

- Subject ID
- Disease/histology
- Protocol number and title
- Date of the AE occurrence
- Describe the nature of the AE (i.e., dermatitis)
- The grade of the AE determined by CTCAE V5.0
- Relationship of the AE to treatment
- Whether the AE was expected or unexpected
- The intervention to address the AE
- A description of the subject's condition
- Outcome
- Indication if the subject remains on the study
- If an amendment will need to be made to the protocol and/or consent form

The PI's signature and date are required on this report.

If an ongoing SAE change in its intensity or relationship to study treatment or if new information becomes available, a follow-up SAE report should be sent within 72 business hours to MCI Multisite Research Program using the same procedure used for transmitting the initial SAE report.

Any local incident, experience or outcome that is (a) unanticipated in terms of nature, severity, or frequency given the research procedures that are described in the protocol-related documents, such as the IRB approve protocol and informed consent document; and the characteristics of the subject population being studied; and (b) Suggest that the research places subject(s) or others at a greater risk of harm (including physical, psychological, economic, or social harm) related to the research, are considered Unanticipated Problems (UPs) involving risks to subjects or others.

All Safety Reports that meet the following criteria are considered UPs involving risk to subjects: Unexpected, related or possibly related to participation in the research as determined by Sponsor Investigator and is Serious.

UPs must be submitted to MCI Multisite Program following the SAEs reporting procedures.

All SAEs and UPs will be reported to IRB of record in accordance with its policies and procedures.

### 11.3 Management of adverse events

Supportive care should be given according to routine clinical practice to manage AEs.

### 11.4 Data Safety Monitoring Committee

The MCI Data Safety and Monitoring Committee (DSMC) will monitor this clinical trial according to the MCI Data and Safety Monitoring Plan (DSMP). In its oversight capacity, the MCI DSMC bears responsibility for suspending or recommending continuation of this study.

DSMC oversight of study conduct includes ongoing review of adverse event data, and periodic review of feasibility and tolerability of study treatment. The guidelines appearing in Section 11 of this protocol are offered for DSMC consideration in assessing adverse events and study objectives. In addition, the DSMC will review reports from all audits, site visits, or study reviews pertaining to this clinical trial and take appropriate action.

The DSMC will review toxicity outcomes after the first 4 patients are enrolled and have at least 90 days of follow-up after completion of study therapy.

If any grade 3-5 toxicity is reported, the DSMC will determine if such toxicity is related to treatment. If the DSMC deems that toxicity rates are excessive then it can, at its discretion, recommend cessation of the trial, dose adjustment, or exclusion of certain treatment sites that are deemed as high-risk for complications.

### 11.5 Early study closure

If >4 patients have grade 3+ toxicity within 90 days of treatment completion, or if any patient has grade 5 toxicity as a result of study therapy, then the study will close as tolerability will not have been demonstrated.

### 11.6 Pregnancy

If it becomes known that a subject is pregnant or may have been pregnant at the time of study participation, the investigator must immediately notify MCI Multisite Research Office via email to [[contact]](mailto:[contact]), the PI ([name] at [contact], and the Institutional Review Board of record (BHSF-IRB at [contact]), and the patient will be discontinued from study participation.

### 11.7 Overdose or misadministration of radiation

Overdose or misadministration of radiation is defined as the accidental or intentional administration of any dose of radiation considered excessive and medically important. All occurrences of overdose or misadministration must be reported as an SAE.

## 12. PATIENT DISCONTINUATION AND REPLACEMENT

### 12.1 Patient discontinuation

Permanent withdrawal of a patient from the study will occur when any of the following occur pertaining to the subject in question:

- Patient withdraws consent or is lost to follow-up.
- Patient becomes pregnant or has the intent to become pregnant.
- Patient is non-compliant with requirements of this study (i.e., refusal to adhere to scheduled visits) that in the opinion of the investigator warrants study withdrawal.
- AE occurs that in the opinion of the investigator is a contraindication to further treatment on study.
- Study closure.
- Death

If a patient is thought to be lost to follow-up, at least 3 documented attempts must be made to contact the patient before deemed lost to follow up. Any subject that is permanently discontinued from study participation will still be followed for safety and will also continue to have protocol-specified follow up evaluation, unless the subject withdraws consent, is lost to follow-up or enrolled in another clinical study.

Subjects who do not return to the treating institution for evaluations required by the study protocol will be offered telephone follow up every 3 months.

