### 12.2 Patient replacement

Any patient that discontinues participation in this study for any reason other than unacceptable toxicity or progressive disease before the initial efficacy evaluation (CT scan 6 weeks after SABR lesion) may be replaced. These cases will be recorded and accounted for in the report of the trial.

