#### 13.3 Secondary objectives

1-year local control (LC) will be assessed according to RECIST 1.1 criteria and will be estimated using the Kaplan-Meier method along with the corresponding 95% confidence interval from the time of study treatment

1-year overall survival (OS) will be estimated using the Kaplan-Meier method along with the corresponding 95% confidence interval from the time of study treatment

The proportion of patients who experience acute grade 3 or higher toxicity attributable to SABR will be determined along with the corresponding 95% confidence interval. For patients receiving SABR to multiple lesions, acute toxicity will be determined from the date of the initiation of SABR.

Patient-reported quality of life will be determined using the FACT-G survey instrument prior to and after SABR.

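### Section 12.1 ends follow-up of a discontinued patient who joins another study, so 1-year overall survival may be censored at a point linked to prognosis

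*Combined protocol and SAP*

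**What the plan says.** **Section 12.1.** It lists the events that lead to permanent withdrawal: "Permanent withdrawal of a patient from the study will occur when any of the following occur". The list covers consent withdrawal or loss to follow-up, pregnancy, non-compliance, an adverse event, study closure and death. By default, a discontinued subject "will still be followed for safety and will also continue to have protocol-specified follow up evaluation". Three events switch this default off, and the third is the one at issue here: the rule applies "unless the subject withdraws consent, is lost to follow-up or enrolled in another clinical study". Separately, subjects who do not come back for evaluations "will be offered telephone follow up every 3 months".

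**Section 12.2.** Replacement is allowed for a patient who discontinues "for any reason other than unacceptable toxicity or progressive disease before the initial efficacy evaluation". This treats progressive disease as a possible reason for discontinuing, although 12.1 does not list it.

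**Section 13.3.** "1-year overall survival (OS) will be estimated using the Kaplan-Meier method along with the corresponding 95% confidence interval", counted from study treatment. For LC, "1-year local control (LC) will be assessed according to RECIST 1.1 criteria and will be estimated using the Kaplan-Meier method". The section gives no censoring rule, no separate vital-status follow-up and no sensitivity analysis for either endpoint.

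**Other sections.** Section 6.11 excludes investigational agents within 2 weeks before or after radiation. Section 11.1 requires adverse events to be collected for at least 100 days after radiation. Sections 2.2 and 13.2 judge tolerability on grade 3 or higher acute toxicity within 90 days.

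**The concern.** The first two exceptions in 12.1 are real barriers to data. The third is not: the patient is still consented and traceable, so the rule gives up data that could be obtained.

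Kaplan-Meier assumes that a patient censored at a given time has the same later risk as those still under observation. A patient who has stopped this study and joined another may well have done so because the disease progressed, and is then likely to have a higher risk of death than those who remain. This is foreseeable. Eligible patients may have metastatic carcinoma with up to 10 treated lesions, the required life expectancy is 6 months against a 12-month endpoint, and another study's agent can begin 2 weeks after radiation.

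Two things are at stake: the accuracy of 1-year OS, and the completeness of the toxicity data behind the tolerability criterion.

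**Working it through.** **Plan's own figures.** The documents state no expected OS or LC rate, so there is no survival figure to reproduce. The operating characteristics in 13.4 do reproduce by exact binomial calculation with n = 30. The probability of at most 4 toxic cases is 79.8% at a true rate of 10.5% and 20.0% at 21.4%. The probability of at least 24 feasible cases is 80.2% at 83.9% and 20.0% at 71.3%. The plan states 80%, 20%, 80% and 20%. None of these uses OS or LC.

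**Model for OS (all rates are assumptions).** Patients start without progression, may progress, and may die from either state, with constant monthly hazards h = -ln(1 - 12-month probability)/12. A fraction q of those who progress is discontinued, joins another study and is censored 1 month after progression.

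- 12-month progression: 40% or 60%
- 12-month death without progression: 5%
- 12-month death after progression: 40% or 60%
- q: 10% to 50%

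**Worked case: progression 60%, death after progression 60%, q = 20%, leavers dying at the same rate as other progressors.**

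- Hazards per month: progression and death after progression are each -ln(0.4)/12 = 0.0764; death without progression is -ln(0.95)/12 = 0.00427.
- Alive without progression at 12 months: 0.40 × 0.95 = 0.380.
- Alive after progression at 12 months: 0.0764 × 0.40 × (1 - 0.95)/0.00427 = 0.357.
- True 1-year OS: 0.380 + 0.357 = 73.7% (simulation with 400,000 patients: 73.8%).
- Kaplan-Meier with the leavers censored: 75.9% in simulation, so about 2.1 points too high, with about 3 of 30 patients censored this way.

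**OS error (Kaplan-Meier minus truth).**

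| Later death hazard of those who leave | Scenarios | Error, points |
|---|---|---|
| Same as other progressors | all combinations above | +0.5 to +6.0 |
| Half that of other progressors | 60%/60%, q 10% to 50% | +0.2 to +2.2 |
| Same as patients without progression | 60%/60%, q 20% to 50% | -1.5 to -2.6 |

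If vital status is collected after entry to the other study, the patient is not censored there and this error disappears.

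**LC.** If local progression prompts the new study, the LC event is counted before censoring and no bias arises by this route. If distant progression prompts it, bias arises only if the local failure hazard then changes. The assumptions are 10% local failure at 12 months before distant progression, 60% distant progression, and 20% to 50% of these patients leaving.

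| Local failure hazard after distant progression, relative to before | LC error, points |
|---|---|
| 0.5 times | -0.2 to -0.5 |
| 1 times | 0.0 |
| 2 times | +0.3 to +0.9 |
| 3 times | +0.6 to +1.8 |

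**Toxicity.** The exception ends safety follow-up as well. If a discontinued patient starts another study's agent as soon as 6.11 allows, at day 14, then up to 90 - 14 = 76 days of the tolerability window and 100 - 14 = 86 days of the 11.1 period could go unobserved. Section 11.1 has no matching exception, so the two sections need to be reconciled.

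**The case against.** **Scope.** A reader might infer that any patient who progresses and joins another trial is dropped. The text does not say that. The exception covers only patients already permanently discontinued, and 12.1 names neither progression nor entry to another trial as a reason. Read literally, a patient who joins another trial without being discontinued stays on the visit schedule. This stands and narrows the point. It does not remove it, because 12.2 implies discontinuation for progressive disease, 12.1 allows it for missed visits, and the clause would be idle unless some discontinued patients were expected to enter other studies.

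**Telephone contact.** The 3-monthly call could supply vital status, and no sentence excludes patients in another study from it. But nothing says that it overrides the exception. The text is ambiguous, which is a reason to state the rule.

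**Direction.** Patients fit enough for another trial may do better than other progressors. This stands: the sign of the OS error is not certain.

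**Consequence.** OS and LC are secondary, and the criteria in 13.4 for moving to a phase II/III trial do not use them. With 30 patients and OS near 76%, the 95% half-width is about 1.96 × √(0.76 × 0.24/30) = 15 points. This also stands as a limit on importance. However, a confidence interval does not cover bias, and this bias can be removed at little cost.

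**Conclusion.** The point holds in a limited form. Section 12.1 gives up obtainable follow-up on discontinued patients who join another study, and 13.3 does not say how they enter the OS analysis. OS would most plausibly read too high, by roughly 0 to 6 points. That range rests wholly on assumed rates of progression, death and leaving; if leavers fare as well as patients without progression, OS reads 1.5 to 2.6 points too low. For LC the error is -0.5 to +1.8 points, so no direction can be claimed.

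A reader might infer a much larger error. For example, suppose 90% are alive at 6 months, 9 of those 27 leave then, and later mortality is 50% in leavers and 15% in stayers. Kaplan-Meier gives 0.90 × 0.85 = 76.5%, against a true 0.90 × (18 × 0.85 + 9 × 0.50)/27 = 66.0%, a gap of 10.5 points. The documents supply none of those rates, and the assumed mortality contrast builds in the upward bias.

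The possible cut in toxicity collection before days 90 and 100 follows from the text, but only for a patient who is discontinued and enrolled elsewhere that early.

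**What to change.** **Section 12.1.** Replace the third exception with reduced follow-up to 12 months unless consent is withdrawn:

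- vital status, by chart review or the existing 3-monthly telephone contact, stated to apply to these patients;
- grade 3 or higher toxicity, at least through the 90-day window and the 100-day period in 11.1;
- any standard-of-care scans of treated lesions;
- no mandatory study visits.

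Simply deleting the exception would not do, because these patients would then owe the full schedule of visits, scans, blood tests and questionnaires.

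**Section 13.3.** State that OS is not censored at entry to another study, and report the number, date and reason of such entries.

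**Cost.** A little more data collection, and some later toxicity will need attribution between the two studies' treatments. The sample size and primary criteria stay as they are.

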### 12.2 Patient replacement

Any patient that discontinues participation in this study for any reason other than unacceptable toxicity or progressive disease before the initial efficacy evaluation (CT scan 6 weeks after SABR lesion) may be replaced. These cases will be recorded and accounted for in the report of the trial.

## 13. STATISTICAL METHODS

### 13.1 Evaluation of study objectives

#### 13.2 Primary objectives

The point estimate for feasibility will be reported as a binary variable with its 95% confidence interval. Feasibility will be achieved if all are true:

- Successful completion of treatment to each lesion within 3 working days of intended treatment completion
- Successful completion of treatment to each lesion within 90 minutes from the patient entering the treatment room until treatment completion. Any machine downtime during treatment delivery should be recorded and will not be included when assessing the time for completion of treatment.
- Image guidance verification of treatment delivery within 5 mm of the planned delivery

The point estimate for tolerability will be reported as a binary variable with its 95% confidence interval. Tolerability will be achieved if all are true:

- No greater than 4 of 30 patients experience grade 3 or higher acute toxicity within 90 days of completing SABR
- No grade 5 toxicity is attributed to SABR

#### 13.3 Secondary objectives

1-year local control (LC) will be assessed according to RECIST 1.1 criteria and will be estimated using the Kaplan-Meier method along with the corresponding 95% confidence interval from the time of study treatment

1-year overall survival (OS) will be estimated using the Kaplan-Meier method along with the corresponding 95% confidence interval from the time of study treatment

The proportion of patients who experience acute grade 3 or higher toxicity attributable to SABR will be determined along with the corresponding 95% confidence interval. For patients receiving SABR to multiple lesions, acute toxicity will be determined from the date of the initiation of SABR.

Patient-reported quality of life will be determined using the FACT-G survey instrument prior to and after SABR.

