### 5. PATIENT SELECTION

#### 5.1 Inclusion criteria

1.  $\geq 18$  years of age at the time of study enrollment
2. Biopsy-confirmed primary or metastatic carcinoma with involvement of the lung, liver, adrenal gland, pancreas, kidney, and/or abdominal/pelvic lymph node that would receive SABR
3. Any lesion that would receive SABR is no larger than 5 cm in greatest dimension
4. 1-10 total lesions that would receive SABR
5. If multiple lesions are treated, they must be at least 3 cm apart
6. Eastern Cooperative Oncology Group (ECOG) performance status of 0-2
7. Life expectancy at least 6 months
8. Women of childbearing potential and men must agree to use adequate contraception (hormonal or barrier method of birth control) prior to study entry and for the duration of study participation. Abstinence is acceptable if preferred by patient. Should a woman become pregnant or suspect she is pregnant while participating in this study, she must inform her treating physician immediately.

9. Patients receiving hormonal therapy or immunotherapy such as immune checkpoint inhibitor that had begun at least 4 weeks prior to SABR will be allowed.

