## 9. TREATMENT RESPONSE EVALUATION

### 9.1 Imaging assessment

Patients should have CT scans of the chest, abdomen, and pelvis at 6 weeks ( $\pm 14$  days) if the six weeks visit is being performed, at 3 months ( $\pm 28$  days), 6 months ( $\pm 28$  days), 9 months ( $\pm 28$  days), and 12 months ( $\pm 28$  days) after completion of SABR delivered on this study, or more often as clinically indicated. IV and/or oral contrast should be used as per treating physician discretion and should be strongly considered if doing so would be critical for clearly visualizing the treated lesion to assess local response.

If a patient has a contraindication to contrast for a CT scan, then an alternate scan should be considered such as PET/CT or MRI.

Treatment response will be evaluated using the Response Evaluation Criteria in Solid Tumors (RECIST) guideline, version 1.1.

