### 9.2 Definitions for disease assessment

- Measurable lesions: Lesions that can be accurately measured in at least one dimension with longest diameter at least 10 mm.
- Malignant lymph nodes: A lymph node will be considered measurable if it measures at least 15 mm in short axis.
- Non-measurable lesions: All other lesions <10 mm or lymph nodes <15 mm in short axis.
- Target lesions: Target lesions should be identified and measured at baseline. Target lesions include measurable lesions up to a maximum of two lesions per organ and up to five lesions in total that are representative of all involved organs. Target lesions should be selected on the basis of their size (lesions with the longest diameter) and are to undergo reproducible repeated measurements. If the largest lesion does not lend itself to reproducible measurement, it should not be considered a target lesion and instead the next largest lesion that can be measured reproducibly should be selected. A sum of the longest diameters for all target lesions will be calculated and reported as the baseline sum diameters. The baseline sum diameters will be used as reference to further characterize any objective tumor regression in the measurable dimension of the disease.
- Non-target lesions: All other lesions (or sites of disease) including any measurable lesions over and above the 5 target lesions should be identified as non-target lesions and should also be recorded at baseline. Measurements of these lesions are not required, but the presence, absence, or in rare cases unequivocal progression of each should be noted throughout follow-up.

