## 9.3 Definitions of Disease Response

Definition of response in target lesions:

- **Complete Response (CR):** Disappearance of all target lesions
- **Partial Response (PR):** At least a 30% decrease in the sum of the diameters of target lesions, taking as reference the baseline sum diameters
- **Local Progressive Disease (LPD):** At least a 20% increase in the sum of the diameters of target lesions compared to baseline sum of target lesions, taking as reference the smallest sum on study (this includes the baseline sum if that is the smallest on study). The sum must also demonstrate an absolute increase of at least 5 mm in addition to the relative increase of 20%.
- **Distant Progressive Disease (DPD):** The appearance of at least 1 new lesion.
- **Stable Disease (SD):** Neither sufficient decrease to qualify as a PR or sufficient increase to qualify as PD, taking as reference the smallest sum diameters while on study.

Definition of response in non-target lesions:

- **Complete Response (CR):** Disappearance of all target lesions
- **Progressive Disease (PD):** Appearance of one or more new lesions and/or unequivocal progression of existing non-target lesions
- **Incomplete Response/Stable Disease (SD):** Persistence of one or more non-target lesions

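### Local control has no event defined per treated lesion, and the only local category is a change in a capped sum of target lesions

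*Combined protocol and SAP*

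**What the plan says.** Section 13.3, repeated in the Protocol Summary, states that "1-year local control (LC) will be assessed according to RECIST 1.1 criteria and will be estimated using the Kaplan-Meier method", with time running from study treatment. It does not say what counts as a local failure, whether the unit is the lesion or the patient, or what happens to a patient who dies without one.

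The response categories are in 9.3. LPD is the only one labelled local: "At least a 20% increase in the sum of the diameters of target lesions compared to baseline sum of target lesions", with an absolute rise of at least 5 mm, also in the sum. Progression among non-target lesions is called PD and covers "Appearance of one or more new lesions and/or unequivocal progression of existing non-target lesions".

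Section 9.2 decides what enters the sum: "Target lesions include measurable lesions up to a maximum of two lesions per organ and up to five lesions in total". Lesions are chosen by size and reproducibility. They must be at least 10 mm, or 15 mm in short axis for nodes. All others are non-target: "Measurements of these lesions are not required", although presence, absence or unequivocal progression of each must be noted.

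Eligibility in 5.1 sets only upper limits on what is treated: "Any lesion that would receive SABR is no larger than 5 cm in greatest dimension" and "1-10 total lesions that would receive SABR". Section 6.10 accepts that lesions not treated on study may be present. Section 9.1 advises contrast where it is "critical for clearly visualizing the treated lesion to assess local response".

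**The concern.** Local control should show whether the irradiated lesions stayed controlled. A change in a sum over a restricted set of lesions answers a different question. Three gaps follow if LPD is the event.

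- **Masking.** Growth of one treated lesion is diluted by other targets that are stable or shrinking.
- **Omission.** A treated lesion that is beyond the cap or too small is non-target. Its unequivocal progression is scored PD, a category shared with new lesions and not labelled local.
- **Untreated lesions.** Nothing in 9.2 keeps a lesion that was not treated on study out of the target set, so its growth can count as local failure.

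Local control is the first-listed secondary objective and the trial's measure of effect on the treated lesion. In affected patients an in-field failure can be reported as control, or the reverse. Deaths within the year are foreseeable, since 5.1 asks for a life expectancy of only 6 months, so their handling also needs stating.

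**Working it through.** The plan gives no rate or precision for local control, so there is no figure to reproduce. The check applies the 9.3 rule to examples and compares it with the same thresholds applied to one lesion. Lesion sizes are illustrative assumptions.

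**Inputs.** Thresholds of 20% and 5 mm (9.3); cap of two per organ and five in total, with minimum sizes of 10 mm and 15 mm for nodes (9.2); one to ten treated lesions, maximum 5 cm, no minimum (5.1); 30 patients (13.4).

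**Masking.** Let one lesion of diameter d grow while the other k − 1 targets, of equal size, stay stable. Growth needed:

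- sum rule: max(0.2 × k × d, 5 mm)
- per-lesion rule: max(0.2 × d, 5 mm)

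| d | Per lesion | Sum, k = 2 | Sum, k = 3 |
|---|---|---|---|
| 10 mm | 10 + 5 = 15 mm | 10 + 5 = 15 mm | 10 + 6 = 16 mm |
| 20 mm | 20 + 5 = 25 mm | 20 + 8 = 28 mm | 20 + 12 = 32 mm |
| 30 mm | 30 + 6 = 36 mm | 30 + 12 = 42 mm | 30 + 18 = 48 mm |

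Once k × d is at least 25 mm, the lesion must grow by k × 20%: 40% with two targets, 60% with three. With five 20 mm targets it must grow by 0.2 × 5 × 20 = 20 mm, that is, double. With k = 1 the two rules are identical at every size.

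**Offset.** Of two 20 mm targets, one shrinks to 14 mm and the other grows to 26 mm. Judged alone, the second has grown by 6 mm and 26/20 − 1 = 30%, a failure. The sum is 14 + 26 = 40 mm, a 0% change from baseline. If the shrinkage was seen first, the smallest sum is 14 + 20 = 34 mm and the rise is 6 mm, 6/34 = 17.6%. Neither is LPD.

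**Untreated growth.** A treated lesion is stable at 20 mm and an untreated target grows from 20 to 28 mm. The sum goes from 40 to 48 mm, +20% and +8 mm, which is LPD although the treated lesion is controlled.

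**Cap.** Of three treated lesions in one organ, at least one is outside the sum. Of ten, at most five can be in it, or two if all are in one organ, so 5 to 8 cannot contribute to LPD. Treated lesions under 10 mm, or nodes under 15 mm in short axis, never can.

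**Weight of one patient.** 1/30 = 3.3 percentage points of 1-year local control, without censoring.

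**The case against.** No section says that LPD is the local-control event, and every example above assumes it. The contrast advice in 9.1 suggests that the intent is the treated lesion; read that way, none of the three errors arises. That limits how firmly the mechanism can be asserted, but without LPD local control has no event definition at all. An intention visible only in contrast advice may also be applied differently across up to five sites.

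Much of the raw information should exist. Forming the sum requires each target's own diameter, and 9.2 requires the status of each non-target lesion to be noted. An in-field failure is therefore lost only if the analyst uses LPD and ignores non-target progression. This is fair, but no rule links those records to local control, and diameters of treated non-target lesions are not required.

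The documents give no distribution of lesion number, size or untreated disease, so the bias may be small. The endpoint is descriptive, 30 patients were chosen pragmatically, and an interval at this sample size is wide: Table 1 gives 73% to 98% for 27 of 30. This bears on severity. A wide interval does not remove a bias.

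A per-lesion rule has its own cost: spurious calls accumulate with lesion count. At an assumed 3% per independent lesion, one lesion gives 3% and ten give 1 − 0.97^10 = 26%. The 5 mm floor limits this but does not abolish it.

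**Conclusion.** The concern holds. It is certain that the plan defines neither the event nor the unit for local control. If the only local category is used as written, misclassification can occur in both directions. It affects patients with several lesions, treated lesions too small to measure, or untreated measurable lesions. The rule works when the single treated lesion is the only measurable one.

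The size per affected patient is about 3.3 points without censoring; the number affected, and so the net direction, cannot be derived from the documents. The examples rest on assumed lesion sizes and on LPD as the event. Local control enters neither the advancement criteria in 13.4 nor the closure rule in 11.5, so the primary conclusions are untouched. This should be fixed, but it does not threaten the trial's main purpose.

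**What to change.** - **9.2.** Record every lesion treated on study at baseline and measure it on each scheduled scan, whether or not it is a RECIST target. State the axis for nodes, because 9.2 uses short axis for measurability but sums longest diameters.
- **9.3 and 13.3.** Define local failure of a treated lesion as an increase of at least 20% and at least 5 mm over that lesion's own smallest diameter, baseline included, in the same axis; for a lesion too small to measure, use unequivocal growth. Exclude lesions not treated on study and apply no cap.
- **13.3.** Define patient-level local control as time from study treatment to first local failure of any treated lesion. Any lesion-level estimate should use standard errors clustered by patient. State how death without local failure is handled; cumulative incidence with death as a competing event may be added as a supplementary result.
- **Overall response.** Keep the RECIST sum for this purpose only, and settle its reference, since the LPD sentence names both the baseline sum and the smallest sum on study.
- **Protocol Summary.** Repeat the local-control definition.

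The cost is wording in four places, one per-lesion data field and a few more measurements on scans already scheduled. No new scans are needed. The drawback is that a single small diameter is noisier than a sum, and false calls rise with the number of lesions. The rule should be set before analysis.
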